9.5 Study Discontinuation

The research team will discuss discontinuation of the study in the event that participants in either condition experience unanticipated adverse events (e.g., increased active suicidality) over the course of study completion. The DSMB and IRB will be involved in such a discussion.

9.6 Study Completion

Data collection for the study will end by November 30, 2022. Data analysis is expected to occur from December 2022 to May 2023. The study is anticipated to be completed by June 1, 2023.

9.7 Conflict of Interest Management Plan

The independence of this study from any actual or perceived influence, such as by the pharmaceutical industry, is critical. Therefore, any actual conflict of interest of persons who have a role in the design, conduct, analysis, publication, or any aspect of this trial will be disclosed and managed. Furthermore, persons who have a perceived conflict of interest will be required to have such conflicts managed in a way that is appropriate to their participation in the trial. The study leadership in conjunction with the appropriate conflict of interest review committee has established policies and procedures for all study group members to disclose all conflicts of interest and will establish a mechanism for the management of all reported dualities of interest.

All investigators will follow the applicable conflict of interest policies.

9.9 Publication Plan

Upon the completion of data analysis by May 2023, the research team anticipates submitting an initial manuscript for publication by August 31, 2023 that describes the primary efficacy of the study. It will be the MPIs' responsibility for publishing the study results.

10 Appendices

Appendix #	Title	Sections	Topic
1	References	1 & 2	Background & Rationale/Significance

11.1 Table 1 – Visit Schedule Table of Full Study Conditions and Measures

	Online consent for initial online screener	Video Screener on WeChat + At home HIV/STI Testing	Consent Call on WeChat	Randomization Call on WeChat	Visit 1: Baseline surveys (Day 1 ± 7)	Visit 2: Study Intervention (ESTEEM iCBT or Self-Monitoring) (Day 7 to 70-719)	Visit 3: 4-month follow-up surveys (Day 119 ± 126)	Visit 4: 8-month follow-up surveys (Day 126 ± 133)
Informed Consent	X	X	X					
Randomization				X				
Demographics Assessment					X			
Primary Measures								
30-Day TimeLine Follow Back					X		X	X
Decisional Balance for Condom Use Scale					X		X	X
Safer Sex Questionnaire					X		X	X
Past 4-month HIV/STI Testing Questionnaire					X		X	X
Secondary Measures*								
Mental Health Measures					X		X	X
Minority Stress Variables & Collective Self-Esteem Measures					X		X	X
Potential Mechanism Variables					X		X	X
Psychosocial Variable Measures					X		X	X
HIV/STI outcomes		X						X
ESTEEM iCBT Treatment						X (ESTEEM iCBT group ONLY)		
Weekly self-monitoring of mood and minority stress						X		
Adverse Event Reporting		X			X	X	X	X

* = See Section 4.2.2. for a full list of secondary measures

6.4 Power for Exploratory Outcomes

7 INTERIM MONITORING

7.1 Overview

7.2 Safety

8 ANALYTIC PLAN

8.1 Overview

8.2 Comparability of Treatment Groups

8.3 Analysis of Primary Outcome

8.4 Analysis of Secondary Outcomes

8.5 Qualitative Analyses

8.6 Exploratory Analyses

REFERENCES

STATISTICAL ANALYSIS PLAN

STUDY SUMMARY (revised 1.24.23)

Title	Developing Efficient Intervention Technologies to Reduce Stigma-Related Stress, Mental Health Problems, and HIV Risk among Young Chinese MSM
Study Design	The design is a two-arm, parallel-assignment randomized controlled trial design to test the efficacy of an internet-based cognitive behavioral therapy (iCBT), Effective Skills to Empower Effective Men (ESTEEM), in comparison to self-monitoring control. The unit of randomization is the individual.
Study Duration	2.67 years
Trial Sites	Hunan province, China (Central South University)
Objective	The primary objective is to evaluate the preliminary efficacy of a Chinese-adapted version of iCBT ESTEEM on young men who have sex with men's (YMSM) HIV risk behavior compared to self-monitoring control. Secondary outcomes will include HIV social-cognitive risk factors, HIV/STI test results, mental health, universal psychosocial risk factors for mental and behavioral health problems, and minority stress. The secondary objectives of this study are to determine whether baseline minority stress exposure moderates treatment efficacy, such that participants with the most minority stress exposure benefit more from iCBT ESTEEM than from self-monitoring control.
Number of Subjects	120
Main Inclusion Criteria	
 (1) 16-30 years old (2) Live in Hunan province, China (3) Current gender identity as male (4) Report past 12-month sex with men (5) Be confirmed HIV-negative upon at-home testing (6) Report past 3-month condomless/PrEP-less anal sex (7) Past-week symptoms of depression or anxiety using the Brief Symptom Inventory-4, cutoff of 2.5 on either the depression subscale, anxiety subscale, or both (8) No past 3-month mental health services of more than 2 visits per month (9) Weekly access to internet on a laptop, desktop, or tablet device (10) Ability to read, write, and speak in Mandarin (11) Provision of informed consent

STATISTICAL ANALYSIS PLAN

Intervention	
1) ESTEEM iCBT: This online CBT treatment consists of 10 weekly modules that participants will complete over the course of 4 months. Modules contain weekly psychoeducational text and vignettes about minority stress and mental health; brief videos illustrating the CBT skills; and homework exercises that therapists review and provide feedback on. Homework exercises include weekly tracking of stress and mood, practicing new skills (e.g., mindfulness, cognitive restructuring), and exercises related to considering the origins of stress and negative emotions that participants may be experiencing. Therapists provide feedback after each homework assignment, including reviewing each participant's treatment goals as part of the first session's homework. Therapists who support this condition will be instructed to incorporate LGBTQ-specific content and feedback into homework reviews. This intervention was culturally adapted for Chinese YMSM and found to be acceptable and feasible.
 
2) Self-monitoring control: In this control condition, participants will be asked to indicate their past 7-day mood, stress experiences, and mental and behavioral health on an online survey. Participants will record these experiences once per week for 10 weeks.

Duration of Intervention	10 weekly modules in up to 17 weeks (four months)
Primary Outcome	Number of past-30-day condomless anal sex (CAS) acts with primary or casual partners as measured by the Timeline Follow-Back at the 8-month follow-up assessment.
Primary Analysis	We will examine the efficacy of the intervention using a generalized linear mixed model to test whether receipt of ESTEEM iCBT vs the self-monitoring control affects changes in the number of past-30 day CAS with primary or casual partners from baseline to 8-month follow up.

STATISTICAL ANALYSIS PLAN

Secondary Outcomes	
Change from baseline to immediate post-intervention (4-month follow-up): Number of past-30-day CAS acts with primary or casual partners (TLFB), number of past-30-day CAS acts with casual partners (TLFB), safer sex self-efficacy (SSQ), decisional balance for condom use (DBCUS), past 4-month HIV/STI testing, depressive symptoms (PHQ-9), anxiety symptoms (GAD-7), alcohol use problems (AUDIT), drug use problems (DUDIT), suicidality (SIDAS), concealment motivation (LGBIS), acceptance concerns (LGBIS), internalized homonegativity (LGBIS), emotion dysregulation (DERS), social support (MSPSS), and rumination (RRS).
 
Change from baseline to 8-month follow up: Number of past-30-day CAS acts with only casual partners (TLFB), safer sex self-efficacy (SSQ), decisional balance for condom use (DBCUS), past 4-month HIV/STI testing, depressive symptoms (PHQ-9), anxiety symptoms (GAD-7), alcohol use problems (AUDIT), drug use problems (DUDIT), suicidality (SIDAS), concealment motivation (LGBIS), acceptance concerns (LGBIS), internalized homonegativity (LGBIS), emotion dysregulation (DERS), social support (MSPSS), rumination (RRS), HIV testing results, and syphilis testing results.

Exploratory Outcomes	
Change from baseline to immediate post-intervention (4-month follow-up): Depression severity and impairment (ODSIS), anxiety severity and impairment (OASIS), self-esteem (RSE).
 
Change from baseline to 8-month follow-up: Depression severity and impairment (ODSIS), anxiety severity and impairment (OASIS), self-esteem (RSE).

STATISTICAL ANALYSIS PLAN

1. BACKGROUND

HIV prevalence among gay, bisexual, and other men who have sex with men (MSM) in China has increased from less than 1.0% in 2003 to 9.2% in 2016.¹ The majority of newly diagnosed MSM are ages 16-30.² Structural and psychological forms of stigma toward young MSM (YMSM) fuel China's HIV epidemic.³⁻⁵ Structurally, Chinese YMSM face a lack of equal rights and legal protections, including no same-sex marriage, same-sex education, or recourse against discrimination.⁶⁻⁸ Not only are YMSM-focused evidence-based treatments lacking in China, but sexual orientation conversion therapy is promoted as a means to help YMSM who are often desperate to maintain heterosexual desires and create traditional families expected by Chinese culture.⁹⁻¹¹ As is true in other countries, this structural stigma gives rise to maladaptive coping processes among YMSM.¹²⁻¹⁴ Known as minority stress, these processes include identity concealment, internalized homonegativity, and sensitivity to identity-based rejection,¹⁵⁻¹⁹ and they drive the substantial mental health disparity borne by YMSM in China.²⁰⁻²⁴ Both minority stress and poor mental health compromise HIV prevention and care behaviors through avoidant coping, low self-worth, impulsivity, and unassertiveness.^{25,26}

Despite the promise of deploying evidence-based interventions to reduce the HIV epidemic among YMSM in China,²⁷ no interventions address this population's minority stress and mental health to prevent HIV. Our team in the US has created such an intervention – ESTEEM (Effective Skills to Empower Effective Men), a minority-stress-focused cognitive-behavioral therapy (CBT) with strong preliminary efficacy across minority stress, mental health, and HIV risk behavior.²⁸⁻³⁰ Yet three features of ESTEEM currently hamper widespread implementation in China or elsewhere. Specifically, ESTEEM: 1) has only been tested in the US without cultural adaptation to high-stigma, non-US contexts, 2) currently requires in-person delivery of 10, 1-hour modules, and 3) has not been reviewed by multi-sector stakeholders to inform barriers and facilitators to its uptake within existing mental and sexual health services, both public and NGO.

2. AIMS

1. **Aim 1:** Evaluate the preliminary efficacy of a Chinese-adapted version of iCBT ESTEEM on young men who have sex with men's (YMSM) HIV risk behavior compared to self-monitoring control. Secondary outcomes will include HIV social-cognitive risk factors, HIV/STI test results, mental health, universal psychosocial risk factors for mental and behavioral health problems, and minority stress.
2. **Aim 2:** Determine whether baseline minority stress exposure moderates treatment efficacy, such that participants with the most minority stress exposure benefit more from iCBT ESTEEM than from self-monitoring control..

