Minority stress underlies substantial mental health disparities affecting Chinese YMSM. Our research shows that stigma gives rise to minority stress reactions including chronic, anxious expectations of rejection; internalized homonegativity; and identity concealment.^{13,14,24,52,53} We estimate that 81% of YMSM in China conceal their sexual orientation from all or most others.⁴¹ Structural stigma in Chinese cultural norms lead a significant proportion of Chinese MSM to have sex with women.^{49,54,55} A meta-analysis showed that 26% of MSM had female sexual partners during the past 6 months and only

26% used condoms then.⁵⁶ An estimated 70% of MSM plan to eventually marry a woman.^{3,56} These identity-related stressors help explain Chinese YMSM's 2-6-times greater odds of depression, anxiety, and alcohol abuse compared to heterosexual men.^{12,24,27,43,57-61}

Minority stress and mental health problems drive Chinese YMSM's HIV risk. Minority stress and poor mental health are clear risks for Chinese YMSM's HIV transmission behaviors.^{12,26-31,50,52,62} Specifically, enacted and internalized stigma predict concealment,²⁴ which in turn predicts lack of HIV-preventative knowledge and behaviors.^{50,63} Minority stress is also associated with emotion dysregulation,⁶⁴⁻⁶⁶ hopelessness,⁶⁷⁻⁶⁹ impulsivity,⁷⁰ poor social support,^{26,71-73} and low self esteem,⁷³ which are also associated with HIV-risk behaviors.^{18,74,75} The mental health consequences of minority stress further predict HIV-risk behaviors: moderate depression is associated with MSM's condomless anal sex (CAS);^{32,76-78} anxiety increases avoiding coping and poor condom use communication;⁷⁹⁻⁸¹ and substance use encourages impulsive sexual behaviors.⁸²⁻⁸⁴

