3.3 Objectives

The primary objective is to evaluate the preliminary efficacy of a Chinese-adapted version of iCBT ESTEEM on YMSM's sexual health and HIV risk behavior.

The secondary objectives of this study are to determine whether iCBT ESTEEM impacts HIV/STI results and symptoms of depression and anxiety, as well as whether baseline minority stress exposure moderates treatment efficacy, such that participants with the most minority stress exposure benefit more from iCBT ESTEEM than those in the self-monitoring

of stress and mood condition. An additional objective is to identify individual and institutional implementation barriers and facilitators of iCBT ESTEEM among Chinese YMSM.

4 Study Design

Aim 2 of the proposed prospective study will follow a 2-arm RCT design where 120 Chinese YMSM participants will be randomly assigned to one of two conditions:

- 1) ESTEEM iCBT: This online CBT treatment consists of 10 weekly modules that participants will complete over the course of 10 weeks. Modules contain weekly psychoeducational text and vignettes about minority stress and mental health; brief videos illustrating the CBT skills; and homework exercises that therapists review and provide feedback on. Homework exercises include weekly tracking of stressful situations and mood, practicing new skills (e.g., mindfulness, cognitive restructuring), and exercises related to considering the origins of stress and negative emotions that participants may be experiencing. Therapists provide feedback after each homework assignment, including reviewing each participant's treatment goals as part of the first session's homework. Therapists who support this condition will be instructed to incorporate SGM-specific content and feedback into homework reviews. Therapists will be mental health counselors in [name] lab at CSU who possess an advanced degree in a mental health field with significant prior experience treating Chinese YMSM with sexual and mental health concerns. In the US, modules were adapted directly from the in-person materials (e.g., therapist manual, participant handouts) used in our previously successful trials of this treatment. The treatment has also been recently, culturally adapted for in-person treatment among Chinese YMSM and found to be acceptable and feasible.

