- 2) Self-monitoring control: In this control condition, participants will be asked to indicate their past 7-day mood, stress experiences, and mental and behavioral health on an online survey. This type of self-monitoring has been shown to yield improvement in behavioral health outcomes. Self-reporting SGM stress experiences has also been shown to produce reductions in depression symptoms over time. Participants will record these experiences once per week for 10 weeks.

[figure not shown]
Prior to randomization, participants will complete an online screener, video screener on WeChat, at-home HIV/STI testing kit for HIV and syphilis, and consent call on WeChat (see Section 6.1 Study Procedures for more information about these steps of the study). For the at-home HIV/STI testing kit for HIV and syphilis, rapid test results will be ready to be read by participants in 20 minutes. HIV/STI test results will be discussed with participants by study counselors during the same day as testing via WeChat. A CSU research team member will contact participants on WeChat after 5 business days of sending the HIV/STI testing kit if the participant has not sent the CSU team a photo of their results. Specific procedures regarding risks for the at-home HIV/STI testing is outlined in Section 2.2.

To assess intervention efficacy, participants will be assessed at three time-points: baseline, immediately post-treatment (4-month follow-up), and 8-month follow-up. Participants will complete validated measures online of past-30-day HIV-risk behavior (e.g., condomless anal sex), mental health (e.g., depression, anxiety), and minority stressors (e.g., discrimination) at all three times points. At 8-month follow-up, participants will be mailed and asked to complete the same at-home HIV/STI testing kit for HIB and syphilis described above.

After completing the baseline assessment, participants randomized to ESTEEM iCBT will be assigned a study therapist and will be contacted by their therapist to schedule a 30-minute

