- Life History Interview of ACEs – 10-items assessing whether participants have experienced different types ACES throughout their lives. The Chinese version of the measure will be used for the present study.
- COVID-19 Questionnaire – 21 questions adapted from prior research by PI [name] for the current study. The questionnaire consists of 9 multiple-choice questions assessing participants' experiences related to the COVID-19 pandemic, including diagnosis with COVID-19 and district lockdowns, and 6 items based on a 10-point Likert scale assessing perceived impact of the pandemic on health and behaviors, with 6 follow-up questions to discern the direction of impact. A translated version of all measures will be used for the present study.
- HIV/STI outcomes (only at pre-baseline [between video screener and consent video call] and 8-month follow-up):
 - At-home HIV/STI testing kit for HIV and syphilis – see Section 6.1 Study Procedures for more information about the at-home HIV/STI testing kit

The following are the weekly assessments that will be administered for 10 weeks on the iCBT online platform to both the ESTEEM iCBT and self-monitoring conditions:

- Weekly surveys
 - Overall Depression Severity & Impairment Scale – see description above.
 - Overall Anxiety Severity & Impairment Scale - see description above.
 - Tracking Minority Stress Experiences Questionnaire – 14-items (13 on a Likert scale and 1 open-ended response item) assessing different type of sexual minority related stressors in the past week. A translated version of the measure in Chinese will be developed for the present study.

For the pilot study, the 10 YMSM will complete the following:

- Brief questionnaire – 5-items assessing participants' feedback on the usability of each session module
- Follow-up interview after completing all 10 modules – an approximately 1-hour interview via WeChat with an RA at CSU asking questions about participants' feedback on the ESTEEM iCBT treatment in terms of comprehension and usability, as well as about the 30-day Timeline Follow-Back assessment
- 30-Day Timeline Follow-Back – see above for a description of this measure

For Aim 3, we will additionally review data for the following:

- Number of sessions completed by participants
- Points of study drop-off
- Acceptability and feasibility – participants' written responses to prompts within online modules will be coded for engagement and relevance to module content

5 Study Participants

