8.4.3.1 Moderation Analyses of Treatment Efficacy

Analysis	In these models, we will examine baseline depression (PHQ-9), anxiety (GAD-7), and minority stressors including concealment motivation (LGBIS), acceptance concerns (LGBIS), and internalized homonegativity (LGBIS) as potential moderators of
----------	---

STATISTICAL ANALYSIS PLAN

	ESTEEM iCBT efficacy, hypothesizing that YMSM with higher baseline depression, anxiety, and minority stress benefit most.
Analysis population	All participants
Endpoint	Immediate post-intervention (4-month follow-up) and 8-month follow-up
Unit of analysis	Participant
Method of analysis	
For all moderators (i.e., depression, anxiety, concealment motivation, acceptance concerns, and internalized homonegativity), a linear mixed model analysis will be performed. Moderation analysis models will include terms for condition, time, moderator, Condition X Time, Condition X Moderator, Time X Moderator, and Condition X Time X Moderator. To probe significant three-way interactions, we will perform simple slopes analyses and differences in slopes will be compared using z-score transformations.³⁵
 
We will test the best-fitting correlation structure, but based on our previous studies, expect it to be compound symmetrical. In the event of high skew or zero inflation, the appropriateness of modeling a negative binomial or Poisson distribution will be considered.

Handling of missing data	MAR assumption
Adjustment covariates	Adjustment for baseline covariates not balanced at randomization
Type I error	5% (2-sided)
Control of type I error	To control for the false discovery rate, we will apply a Bonferroni correction for each set of moderators (e.g., mental health, minority stress). Primary interpretation will focus on effect sizes.
Treatment effect estimate	Odds ratio with 95% confidence limits

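### Aim 2 names baseline minority stress exposure as the moderator, but the minority-stress moderators in SAP 8.4.3.1 are all reaction scales, so the analysis as specified does not test the stated aim

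*SAP*

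**What the plan says.** **The objective.** SAP Section 2 gives Aim 2 as "Determine whether baseline minority stress exposure moderates treatment efficacy, such that participants with the most minority stress exposure benefit more from iCBT ESTEEM", with self-monitoring as the comparator. Protocol 3.3 likewise asks "whether baseline minority stress exposure moderates treatment efficacy", with the expectation that the most exposed participants gain most. The Protocol Synopsis, Protocol 7.3 and the SAP study summary also state the moderator as exposure.

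**The analysis.** SAP 8.4.3.1 tests baseline PHQ-9, GAD-7 and "minority stressors including concealment motivation (LGBIS), acceptance concerns (LGBIS), and internalized homonegativity (LGBIS) as potential moderators of" efficacy. No other minority-stress moderator is named there. The lead-in text of SAP 8.4.3 stops in mid-sentence and adds nothing.

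**The measurement.** Protocol Section 4 says that participants complete validated measures of "minority stressors (e.g., discrimination) at all three times points", and the Synopsis says the same. The Tracking Minority Stress Experiences Questionnaire is described in Protocol 4.2.2 as "assessing different type of sexual minority related stressors in the past week". It is listed there under the weekly platform surveys, not under the baseline, 4-month and 8-month battery.

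**The concern.** Exposure to stigma (events such as discrimination) and the internal response to it (concealing, expecting rejection, devaluing oneself) are different constructs, and the Protocol's rationale separates them. Protocol 2.1 says that "stigma gives rise to minority stress reactions including chronic, anxious expectations of rejection; internalized homonegativity; and identity concealment". Those reactions correspond closely to the three LGBIS subscales that serve as moderators.

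An interaction between arm and a baseline LGBIS score shows whether men with stronger internal reactions respond more to a treatment aimed at those reactions. It does not show whether men who met more stigma respond more. If the analysis is run as specified and reported under the aim as worded, a positive result would be read as evidence that the most exposed men benefit most, and a null result as evidence that they do not. Neither reading follows. The two would also point to different groups if the intervention were later targeted.

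**Working it through.** This is a question of construct and timing, so the check traces the objective through the moderators to the baseline instruments.

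1. **Construct in the objective.** It is exposure, in all five places listed above.

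2. **Construct in the analysis.** SAP 8.4.3.1 has five moderators. Two are symptom scales (PHQ-9, GAD-7). The other three compare with the documents' own descriptions as follows:

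| LGBIS subscale | Description elsewhere in the documents |
|---|---|
| Concealment motivation | Identity concealment: a reaction (Protocol 2.1); a coping process (SAP Section 1) |
| Acceptance concerns | Said to assess rejection sensitivity (Protocol 4.2.2); anxious expectation of rejection is a reaction (Protocol 2.1) |
| Internalized homonegativity | A reaction (Protocol 2.1); a coping process (SAP Section 1) |

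SAP 4.2 also groups the three as minority stress mechanism outcomes. So 3 of 3 minority-stress moderators are reactions, and 0 of 5 moderators measure exposure.

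3. **Named baseline instruments.** The visit schedule (Protocol 11.1) has a generic baseline row for minority stress variables, and its footnote sends the reader to Section 4.2.2 for the full list of secondary measures. That list contains no discrimination scale or minority-stress event scale, and neither does SAP Table 1. The adverse childhood experiences interview is given at baseline, but it covers childhood adversity and is not a planned moderator.

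4. **Timing of the one experience measure.** Under Protocol 6.1 the baseline surveys are completed before the randomization call. The Tracking questionnaire runs weekly for 10 weeks in both arms, in the intervention column of the schedule that starts at Day 7. Its scores are post-randomization and could be affected by arm, so they cannot stand in for a baseline moderator.

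5. **The conflict that remains.** Steps 3 and 4 do not fit the two Protocol statements that discrimination-type stressors are assessed at all three time points. Either such a measure was taken and both the measure lists and SAP 8.4.3.1 leave it out, or it was not taken and those statements are wrong.

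**The plan's own figure.** Protocol 7.2.1 claims at least 0.80 power for a medium moderator effect, printed as 0.15. Reading 0.15 as Cohen's f², take one interaction term in a model with three predictors, two-sided alpha 0.05, and noncentrality f² × N:

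- N = 120: 0.15 × 120 = 18.0, power 0.988.
- N = 96 (120 × 0.80, after 20% attrition): 0.15 × 96 = 14.4, power 0.964.

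On that reading the claim reproduces for a two-way interaction. It does not bear on this point, because power for an LGBIS moderator says nothing about which construct is tested.

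**The case against.** **The terms are loose, and the analysis text is consistent with itself.** Protocol 5.1 and the Synopsis give concealment as an example of a minority stressor. Protocol 1.1 and SAP Section 1 define minority stress as these very processes. The hypotheses in Protocol 7.2.1 and SAP 8.4.3.1 speak of higher baseline minority stress without the word exposure. On that usage, calling the LGBIS subscales stressors is not an unexplained substitution. This stands as far as it goes: part of the problem is inconsistent vocabulary. It does not rescue the aim, which says exposure, while Protocol Section 4 uses stressors to mean discrimination. A reader could therefore take a reaction-based result for a finding about exposure.

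**A reader might infer that exposure was never measured at baseline and that Aim 2 cannot be answered.** The documents do not support that. Two Protocol statements say the opposite. The full instrument set is in a measures packet that is not among these documents. The itemised list is also not a perfect guide: the schedule row mentions collective self-esteem, for which 4.2.2 names no scale. What can be said is that no such instrument is named.

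**A reader might try to size the loss by treating the LGBIS scores as a proxy for exposure.** The documents give no correlation between the two, so any such figure would only reflect the value assumed.

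**A reader might object that the same subscales are also secondary outcomes.** That is not a defect. Baseline values precede randomization, and using them as moderators is ordinary practice.

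**Conclusion.** The concern holds as a mismatch between aim and analysis. None of the minority-stress moderators in SAP 8.4.3.1 measures the exposure named in Protocol 3.3 and SAP Aim 2, and no baseline exposure instrument is named in either measure list. The analysis as specified therefore does not test Aim 2 as stated. It can still answer a related question, about baseline reactions.

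The conclusion rests on the documents' own classification of the three constructs and on Section 4.2.2 being the full list that the schedule footnote says it is. It would change in part if the measures packet contains a baseline discrimination scale. The aim could then be tested, but the SAP would still have to name that scale. The consequence is confined to a secondary objective and to what may be concluded from it; the primary analysis is unaffected.

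**What to change.** First check the baseline survey as it was administered. New baseline items are no longer possible: the SAP, revised 1.24.23, reports 120 participants enrolled and randomized.

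- **If a baseline discrimination measure was collected:** name the instrument and its score in SAP 8.4.3.1 as the Aim 2 exposure moderator, and add it to Protocol 4.2.2 and SAP Table 1. Keep the three LGBIS subscales under a separate label, as minority stress reactions.
- **If it was not:** replace exposure in Protocol 3.3, SAP Aim 2, the SAP study summary and the conclusions with baseline minority stress reactions (concealment motivation, acceptance concerns, internalized homonegativity). Make the same change in the Protocol Synopsis and 7.3. Correct the statements about discrimination in the Synopsis and in Protocol Section 4.

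Either change should be dated and made before moderator results by arm are seen.

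The cost is small. In the first case it is one more moderator. SAP 8.4.3.1 applies Bonferroni within each set of moderators, so if exposure joined the minority stress set the per-test level would move from 0.05/3 = 0.0167 to 0.05/4 = 0.0125. If exposure forms its own set, the level for the LGBIS subscales does not change; the SAP should say which applies. In the second case the cost is a narrower stated conclusion.
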